If a safety issue occurring in one of the sub-studies is evaluated relevant for the other sub-studies the necessary actions will be implemented for all relevant sub-studies.

Furthermore, all four indications are often treated by the same medical specialists. Therefore, the clinical study sites are likely to cover more or all indications. A well-recognised principle in clinical studies is, that having a reasonable number of patients enrolled in a study at each clinical study site will best ensure the quality of study conduct by the clinical study site staff having more practice, as compared to having very few patients, as would be the case if the indications would be investigated under separate protocols using separate data systems. Furthermore, handling one protocol is most likely less burdensome to the clinical study site staff than handling four individual protocols. The potential advantages of applying a basket study design are supported by a recent review.⁷ Thus, the implementation of a basket study design will optimise the use of operational resources as it will allow for the best utilisation of the expertise by the investigators and the number of sites will be reduced compared to conducting individual studies for the four indications.

To ensure that differences in study conduct between the four indications are recognisable and apparent, the following measures are implemented:

- Thorough study specific training of site staff is conducted by Novo Nordisk before initiation as well as during the study.
- Thorough monitoring of participant data by Novo Nordisk staff to support correct allocation as well as indication-specific protocol compliance. See Section [10.1.8.2](#).
- Appropriate measures during the screening process e.g., automatic system prompts to ensure participants are allocated correctly into the relevant sub-study. See Section [6.3](#).
- Participant numbers are indication-specific, so that site staff should be able to easily recognise what indication a given participant belongs to.
- Indication-specific data are entered in indication-specific eCRF pages.
- Indication-specific procedures are clearly outlined and easily identified throughout this master protocol.
- Trial product and -labelling will be identical to minimise mistakes.

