8.2.4 Transthoracic echocardiogram

A transthoracic echocardiogram (TTE) will be performed for participants with TS or NS.

Any TTE performed within a month prior to screening can be used as baseline data, if the TTE is performed according to the required standards and all relevant parameters are available.

The investigator or a qualified specialist will evaluate the findings from the TTE examination and classify them as either: “normal”, “abnormal, not clinically significant” or “abnormal, clinically significant”. The evaluation and classification will be based on both morphologic and dynamic parameters, as per local practice. Common morphologic parameters are: Left ventricular internal diameter at the end of diastole (LVIDed), Left ventricular internal diameter at the end of systole (LVIDes), End-diastolic interventricular septal thickness (IVSed), End-diastolic left ventricular posterior wall thickness (LVPWed), Left ventricular outflow tract (LVOT) diameter, or right ventricular internal diameter at the end of diastole (RVIDed), whereas dynamic parameters commonly address cardiac output, ejection fraction, and diastolic function.

For the participants with NS, the parameters of interest outlined in [Table 8-3](#) will be recorded in the eCRF.

Table 8-3 Echocardiographic measures to be collected for children with NS

Echocardiographic measures to be collected (NS)	Unit
End-diastolic interventricular septal thickness (IVSed)	mm
End-diastolic left ventricular posterior wall thickness (LVPWed)	mm
Left ventricular internal diameter at the end of diastole (LVIDed)	mm
Left ventricular internal diameter at the end of systole (LVIDes)	mm
Left ventricular mass	g
Left ventricular outflow tract (LVOT) peak gradient	mmHG

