9.3.3 Secondary endpoints/estimands analysis

Supportive Secondary Safety endpoints/estimands

The supportive secondary safety estimand regarding the incidence of AEs possibly or probably related to somapacitan from baseline up to week 26 of somapacitan treatment will be evaluated in a similar way as the primary endpoint including AEs possibly or probably related to somapacitan in the endpoint attribute.

The supportive secondary safety estimand regarding the incidence of AEs from baseline up to week 156 of somapacitan treatment will be evaluated in a similar way as the primary endpoint substituting 156 weeks for 26 weeks.

Supportive Secondary efficacy endpoints/estimands

Table 9-1 Overview of supportive secondary Efficacy endpoints

Title	Time frame	Unit	Details
Height velocity	From baseline (week 0) to visit 7 (week 26).	cm/year	Derived as HV at week 26 = (height at 26 weeks visit – height at baseline)/(time from baseline to 26 weeks visit in years).

Title	Time frame	Unit	Details
Change in Height SDS	From baseline (week 0) to visit 7 (week 26).	Score ^a	
Derived as the Height SDS value at baseline week 0 subtracted from the Height SDS value at week 26 (visit 7).
 
Height SDS is derived as:
 $\text{Height SDS}_i = \frac{\left(\frac{\text{Height}_i}{\text{population median}} \right)^{\text{Skewness}} - 1}{\text{Skewness} * \text{population SD}}$ 
where i indicates the visit. The population median and standard deviation are the ones corresponding to the age at visit i. The population median and standard deviation and skewness are based on reference data.²

Change in Height Velocity SDS	From baseline (week 0) to visit 7 (week 26).	Score ^a	
Derived as the Height Velocity SDS value at baseline week 0 subtracted from the Height Velocity SDS value at week 26 (visit 7). Height Velocity SDS is derived as:
 $\text{HV SDS}_i = \frac{\text{HV}_i - \text{population mean HV}}{\text{population SD}}$ 
where i indicates the visit. The population mean and standard deviation corresponding to the age at visit i. The population mean and standard deviation are based on reference data.^{2,53}

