Midparental target height (MPH)	Screening (visit 1)	cm	Derived as: Girls TH: (mother's height + father's height-13)/2 ⁵⁶ Boys TH: (mother's height + 13 + father's height)/2 ⁵⁶
MPH SDS	Screening (visit 1)	Score ^c	MPH SDS is derived as: $MPH\ SDS = \frac{Fathers\ height\ SDS + mothers\ height\ SDS}{2}$ Where parental height SDS is derived as: $MPH\ SDS = \frac{Height - population\ mean}{population\ SD}$ The population mean and standard deviation comes from reference data. ⁵⁷
Index of genetic height potential	From baseline (week 0) to the visit NAH is reached	Score ^d	Derived as NAH SDS – MPH SDS

Title	Time frame	Unit	Details
Change in interventricular Septum end diastole (IVSed) SDS	From baseline (week 0) to visit 7 (week 26).	Score ^b	
Derived as the IVSed SDS value at baseline week 0 subtracted from IVSed SDS value at week 26 (visit 7) for Turner syndrome.
 
IVSed SDS is derived as:
 $\text{IVSed SDS}_i = \frac{\ln(\text{IVSed})_i - \text{intercept} + \ln(\text{Weight}_i * \text{slope})}{\text{SD residual}}$ 
where i indicates the visit. The intercept, slope and SD residuals are the ones corresponding to the age at visit i. The intercept, slope and SD residuals are based on reference data.⁵⁸

Change in left ventricle posterior wall end diastole (LVPWed) SDS	From baseline (week 0) to visit 7 (week 26).	Score ^b	
Derived as the LVPWed SDS value at baseline week 0 subtracted from LVPWed SDS value at week 26 (visit 7) for Turner syndrome.
 
LVPWed SDS is derived as:
 $\text{LVPWed SDS}_i = \frac{\ln(\text{LVPWed})_i - \text{intercept} + \ln(\text{Weight}_i * \text{slope})}{\text{SD residual}}$ 
where i indicates the visit. The intercept, slope and SD residuals are the ones corresponding to the age at visit i. The intercept, slope and SD residuals are based on reference data.⁵⁸

Change in left ventricle inner dimension end diastole (LVIDed) SDS	From baseline (week 0) to visit 7 (week 26).	Score ^b	
Derived as the LVIDed SDS value at baseline week 0 subtracted from LVIDed SDS value at week 26 (visit 7) for Turner syndrome.
 
LVIDed SDS is derived as:
 $\text{LVIDed SDS}_i = \frac{\ln(\text{LVIDed})_i - \text{intercept} + \ln(\text{Weight}_i * \text{slope})}{\text{SD residual}}$ 
where i indicates the visit. The intercept, slope and SD residuals are the ones corresponding to the age at visit i. The intercept, slope and SD residuals are based on reference data.⁵⁸

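### The four echocardiographic SDS changes are planned for Turner syndrome although numeric recording is specified only for Noonan syndrome, and neither the Protocol nor the SAP formula gives a valid SDS

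*Protocol*

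**What the plan says.** **Which indication is analysed.** Protocol section 9.3.6, Table 9-2, defines the first echocardiographic row as "Derived as the IVSed SDS value at baseline week 0 subtracted from IVSed SDS value at week 26 (visit 7) for Turner syndrome". The LVPWed, LVIDed and LVIDes rows name the same indication, as do all four rows in SAP section 6.1, Appendix 1.

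**Which data are collected.** Section 8.2.4 has the echocardiogram performed in both TS and NS, with a three-category reading for each: "The evaluation and classification will be based on both morphologic and dynamic parameters, as per local practice". On numeric entry it says "For the participants with NS, the parameters of interest outlined in" Table 8-3 go into the eCRF. That table is titled "Echocardiographic measures to be collected for children with NS", and four of its six rows are IVSed, LVPWed, LVIDed and LVIDes. No passage expressly specifies numeric entry for TS.

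**The Protocol formula** has the same form in all four rows:

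`SDS = [ln(measure) - intercept + ln(Weight x slope)] / SD residual`

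On the coefficients it adds: "The intercept, slope and SD residuals are the ones corresponding to the age at visit i". Their values come from a cited echocardiographic reference and are not printed.

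**The SAP formula** is the same, except that ln(measure) is replaced by ln(measure SDS) in all four rows.

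SAP section 4.8 declares no change to the protocol-planned analysis. The SAP is based on Protocol 3.0, and the Protocol's change tables list no later edit to these formulas, so the version difference does not explain the discrepancy.

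**The concern.** There are three separate problems.

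1. The analysis and the specified data collection point to different indications. As written, TS has an SDS change without specified numeric inputs, while NS has the inputs and no planned SDS change.
2. The Protocol formula is not a standardised residual. The plan's other linear scores (height velocity SDS in Table 9-1, parental height SDS in Table 9-2) are observed minus reference. Here only part of the prediction is subtracted and the weight part is added.
3. The SAP formula defines the SDS in terms of itself. The measured dimension no longer appears, and the logarithm does not exist for an SDS of 0 or below.

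The purpose of these parameters is to show whether heart dimensions change beyond what body growth explains. A score that rises with weight cannot do that. Footnote b of Table 9-2 also tells the reader that a positive value means closer to or above the reference, so a weight artefact could be read as a cardiac finding.

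**Working it through.** The plan gives no figure to reproduce. The check is a comparison of passages, then algebra, then an illustration on assumed coefficients.

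**1. Indication**

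| | TS | NS |
|---|---|---|
| Echocardiogram performed (8.2.4) | yes | yes |
| Normal/abnormal classification (8.2.4) | yes | yes |
| Numeric dimensions in eCRF (8.2.4, Table 8-3) | not specified | specified |
| SDS change planned (Table 9-2; SAP Appendix 1) | yes | no |

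The indication labels in Table 9-2 carry meaning. The sitting-height rows name TS and ISS, which matches the collection in section 8.1.1 and the flowchart. The echocardiographic rows do not match theirs. The closing sentence about summarising for relevant indications does not override an explicit label.

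**2. Protocol formula**

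A log-regression SDS is `[ln(Y) - predicted ln(Y)] / SD`. If the prediction is intercept plus weight term, both must be subtracted.

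*Dimension unchanged, coefficients constant.* The printed change is `ln(W1/W0) / SD`, whatever the slope. For a log-log reference with slope b the correct change is `-b ln(W1/W0) / SD`. With a 6% weight gain, ln(1.06) = 0.0583:

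- printed: 0.0583/0.20 = +0.29 to 0.0583/0.10 = +0.58
- correct, b 0.3 to 0.4: -0.3 x 0.0583/0.20 = -0.09 to -0.4 x 0.0583/0.10 = -0.23

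The sign is reversed.

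*Child exactly on the reference.* Assume `lnY = a + b lnW`, with b 0.2 to 0.5 and residual SD 0.10 to 0.20. The correct score is 0. The printed score is `[(1+b) lnW + ln b] / SD`. At 40 kg (lnW = 3.689):

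- b = 0.20, SD 0.20: (4.427 - 1.609)/0.20 = +14.1
- b = 0.35, SD 0.15: (4.980 - 1.050)/0.15 = +26.2
- b = 0.50, SD 0.10: (5.533 - 0.693)/0.10 = +48.4

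A score of 0 at 40 kg would need b of about 0.023.

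*Change for a child who stays on the reference* (true change 0), constant coefficients: `(1+b) ln(1+gain) / SD`.

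- b = 0.20, 3% gain, SD 0.20: 1.20 x 0.0296/0.20 = +0.18
- b = 0.35, 5% gain, SD 0.15: 1.35 x 0.0488/0.15 = +0.44
- b = 0.50, 10% gain, SD 0.10: 1.50 x 0.0953/0.10 = +1.43

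*Age-specific coefficients, as the plan states.* If the slope differs between visits, size and sign can both change. For 40 to 42 kg and SD 0.15:

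- slope 0.40 to 0.35: (-0.1674 + 0.0488 - 0.1335)/0.15 = -1.68
- slope 0.35 to 0.40: +2.58

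From 0.35, a fall of about 0.010 would cancel the rise seen with constant coefficients.

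*A bracket alone is not enough.* Since `ln(Weight x slope) = ln(Weight) + ln(slope)`, the weight coefficient would be fixed at 1. Under the same log-log assumption (35 kg, b 0.3 to 0.4, SD 0.10 to 0.20), a child on the reference would then score -12.8 to -6.1. The weight term itself needs checking against the reference.

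**3. SAP formula**

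The expression has no measured input. Its logarithm fails whenever the SDS is 0 or less. If SDS is normal with SD 1, that is 50% of values at mean 0, 84% at mean -1 and 16% at mean +1.

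**The case against.** **TS values may be captured anyway.** Section 8.2.4 accepts an echocardiogram from before screening as baseline only if all relevant parameters are available, and that sentence covers both indications. Section 9.3.5 plans a summary of echocardiograms for TS and NS as well as a tabulation of the investigator's evaluation, which suggests more than a classification. Section 10.1.8.1 puts participant data on CRFs, and section 4.2 says "Indication-specific data are entered in indication-specific eCRF pages"; those pages are not part of the documents. This is a fair caution. It means the inputs for TS are not expressly specified, not that they are known to be missing. The disagreement between section 8.2.4 and Table 9-2 stands.

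**The SAP error is an obvious slip.** The Protocol prints the raw measure in the same rows, the SAP abbreviation list defines IVSed as a thickness, and the SAP declares no changes. A programmer would guess the intent. However, falling back on the Protocol formula leads to the second error, so the guess does not give a usable definition. The added weight term appears in all eight rows, which makes an isolated typing fault unlikely.

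**The magnitudes rest on assumptions.** This is correct. The slope, residual SD, weight gains and log-log form are all assumed. The large levels come partly from putting a log-log exponent into a term written differently, and nothing in the documents supports a particular slope step within 26 weeks. What survives without a slope value is that, at constant coefficients and an unchanged dimension, the printed score rises with weight.

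**The stakes are small.** These are descriptive parameters with about ten participants per indication and no hypothesis tests. That limits the priority, but the formulas as printed would still give wrong results.

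**Conclusion.** The concern holds in all three parts. The indication named for the four SDS changes disagrees with the indication for which numeric recording is specified. All eight printed formulas add the weight term instead of subtracting it. All four SAP rows take the logarithm of the SDS, so they cannot be programmed as written.

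The structural errors do not depend on any assumed value. The sizes do: +14.1 to +48.4 for a child who should score 0 at 40 kg, and +0.18 to +1.43 for a true change of 0 when coefficients stay constant. With age-specific coefficients the error in the change can go either way.

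The damage is confined to these descriptive parameters. The primary and secondary endpoints, the numeric recording in NS and the planned echocardiogram summaries for TS and NS are unaffected. It should be corrected, but it does not threaten the main results.

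**What to change.** In Protocol Table 9-2 and SAP Appendix 1:

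1. Reconcile the indication with section 8.2.4 and Table 8-3. Either name NS in the four rows, or keep TS and specify numeric eCRF recording of the four dimensions for TS.
2. Print one formula in both documents: `SDS_i = [ln(raw measure_i) - (predicted ln(measure) at Weight_i)] / SD residual`. Put the whole prediction in brackets and check its parameterisation, including how the slope enters, against the cited echocardiographic reference.
3. Record the correction in the SAP before database lock. Section 2.1 allows locks per indication, so the relevant date is that of the indication concerned.

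The cost is text corrections to four rows in each document and one SAP entry. Naming NS needs no new data. Keeping TS needs an eCRF addition if its pages do not already capture the values. Because the SAP was written after first patient first visit, it may also need retrieval of past measurements, some of which may not exist given that the TS reading follows local practice.

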Change in left ventricle inner dimension end systole (LVIDes) SDS	From baseline (week 0) to visit 7 (week 26).	Score ^b	
Derived as the LVIDes SDS value at baseline week 0 subtracted from LVIDes SDS value at week 26 (visit 7) for Turner syndrome.
 
LVIDes SDS is derived as:
 $\text{LVIDes SDS}_i = \frac{\ln(\text{LVIDes})_i - \text{intercept} + \ln(\text{Weight}_i * \text{slope})}{\text{SD residual}}$ 
where i indicates the visit. The intercept, slope and SD residuals are the ones corresponding to the age at visit i. The intercept, slope and SD residuals are based on reference data.⁵⁸

Title	Time frame	Unit	Details
Change in sitting height/height (SH/H)	From baseline (week 0) to visit 7 (week 26).	Ratio	Derived as SH/H at baseline week 0 subtracted from SH/H at week 26 (visit 7) for TS & ISS .
Change in sitting height/height SDS (SH/H SDS)	From baseline (week 0) to visit 7 (week 26).	Ratio	Derived as SH/H SDS at baseline week 0 subtracted from SH/H SDS at week 26 (visit 7) for TS & ISS . SH/H SDS is derived as: $\text{SH/H SDS}_i = \frac{\left(\frac{\text{SH}/H_i}{\text{population median}} \right)^{\text{Skewness}} - 1}{\text{Skewness} * \text{population SD}}$ where i indicates the visit. The population median and standard deviation are the ones corresponding to the age at visit i.
Change in bone age	From screening (visit 1) to visit 9 (week 52).	Ratio	The bone age/chronological age value at screening (visit 1) subtracted from the bone age value at week 52 (visit 9).

^aNegative score indicates that treatment burden is less compared to baseline.

^bPositive score indicates that the value is closer to or above the reference population compared to baseline.

^cNegative values indicate that the values are lower than the reference population.

^dNegative values indicate that the NAH is below the genetic height potential.

^eOnly to be collected from participants switching to somapacitan from daily GH treatment.

Height Velocity at visit 9 (week 52), Change in Height SDS from baseline (week 0) to visit 9 (week 52), Change in Height Velocity SDS from baseline (week 0) to visit 9 (week 52), Change in IGF-1 SDS from baseline (week 0) to visit 9 (week 52) and Change in IGFBP-3 SDS from baseline (week 0) to visit 9 (week 52) will be derived as parameters in the same way as the corresponding secondary endpoints at visit 7 (week 26).

The parameters will be summarised for relevant indications, SGA, TS, NS or ISS.

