#### **4.6 Other Analysis**

##### **4.6.1 Other parameters**

**Table 2 Overview of other parameters**

| Title  | Time frame  | Unit                 |
|--|---|----------------------|
| Child treatment burden measure: GH-INJ-CTB-Physical e                 | Visit 5   | Score a   |
| Child treatment burden measure: GH-INJ-CTB-Emotional Well-being e     | Visit 5   | Score a   |
| Child treatment burden measure: GH-INJ-CTB-Interference e             | Visit 5   | Score a   |
| Child treatment burden measure: GH-INJ-CTB-Overall treatment burden e | Visit 5   | Score a   |
| Patient Preference: GH-PPQ-Child e                                    | Visit 5   | Categorical response |
| Near adult height (NAH)  | 18 months prior to screening to visit 18 (week 156) | Yes/No               |
| Change in height SDS at the visit when NAH is reached                            | From baseline (week 0) to the visit NAH is reached  | Score b   |
| Midparental target height (MPH)  | Screening (visit 1)                                 | cm                   |
| MPH SDS  | Screening (visit 1)                                 | Score c   |
| Index of genetic height potential  | From baseline (week 0) to the visit NAH is reached  | Score d   |
| Change in interventricular Septum end diastole (IVSed) SDS                       | From baseline (week 0) to visit 7 (week 26)         | Score b   |
| Change in left ventricle posterior wall end diastole (LVPWed) SDS                | From baseline (week 0) to visit 7 (week 26)         | Score b   |
| Change in left ventricle inner dimension end diastole (LVIDed) SDS               | From baseline (week 0) to visit 7 (week 26)         | Score b   |
| Change in left ventricle inner dimension end systole (LVIDes) SDS                | From baseline (week 0) to visit 7 (week 26)         | Score b   |
| Change in sitting height/height (SH/H)   | From baseline (week 0) to visit 7 (week 26)         | Ratio                |
| Change in sitting height/height SDS (SH/H SDS)                                   | From baseline (week 0) to visit 7 (week 26)         | Ratio                |
| Change in bone age/chronological age   | From screening (visit 1) to visit 9 (week 52)       | Ratio                |

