| Other parameter | Change in left ventricle inner dimension end diastole (LVIDed) SDS | From baseline (week 0) to visit 7 (week 26)        | Score b | Derived as the LVIDed SDS value at baseline week 0 subtracted from LVIDed SDS value at week 26 (visit 7) for Turner syndrome.

LVIDed SDS is derived as:

$\text{LVIDed SDS}_i = \frac{\ln(\text{LVIDed SDS})_i - \text{intercept} + \ln(\text{Weight}_i * \text{slope})}{\text{SD residual}}$

where i indicates the visit. The intercept, slope and SD residuals are the ones corresponding to the age at visit i. The intercept, slope and SD residuals are based on reference data.  |
| Other parameter | Change in left ventricle inner dimension end systole (LVIDes) SDS  | From baseline (week 0) to visit 7 (week 26)        | Score b | Derived as the LVIDes SDS value at baseline week 0 subtracted from LVIDes SDS value at week 26 (visit 7) for Turner syndrome.

LVIDes SDS is derived as:   |

|                 |  |   |       |   |
|-----------------|--|---|-------|---|
|                 |  |   |       | $\text{LVIDes SDS}_i = \frac{\ln(\text{LVIDes SDS})_i - \text{intercept} + \ln(\text{Weight}_i * \text{slope})}{\text{SD residual}}$ 
where i indicates the visit. The intercept, slope and SD residuals are the ones corresponding to the age at visit i. The intercept, slope and SD residuals are based on reference data.
   |
| Other parameter | Change in sitting height/height (SH/H)         | From baseline (week 0) to visit 7 (week 26)   | Ratio | Derived as SH/H at baseline week 0 subtracted from SH/H at week 26 (visit 7) for TS & ISS .  |
| Other parameter | Change in sitting height/height SDS (SH/H SDS) | From baseline (week 0) to visit 7 (week 26)   | Ratio | 
Derived as SH/H SDS at baseline week 0 subtracted from SH/H SDS at week 26 (visit 7) for TS & ISS.
 
SH/H SDS is derived as:
 $\text{SH/H SDS}_i = \frac{\left( \frac{\text{SH/H}_i}{\text{population median}} \right)^{\text{Skewness}} - 1}{\text{Skewness} * \text{population SD}}$ 
where i indicates the visit. The population median and standard deviation are the ones corresponding to the age at visit i.
 |

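### As written, Noonan syndrome gets no size-adjusted echocardiogram result: the four echo SDS rows are assigned to Turner syndrome and stop at week 26, and their formula needs checking

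*Protocol*

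**What the plan says.** **Collection.** Protocol 8.2.4 gives both TS and NS a transthoracic echocardiogram (TTE) and has it graded in three categories: "The evaluation and classification will be based on both morphologic and dynamic parameters, as per local practice". The rule on recorded numbers names one indication: "For the participants with NS, the parameters of interest outlined in" Table 8-3 go into the eCRF. Table 8-3 lists IVSed, LVPWed, LVIDed, LVIDes, left ventricular mass and LVOT peak gradient.

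**Schedule.** The NS row of the flowchart in protocol 1.2 has TTE at screening, at weeks 26, 52, 78, 104, 130 and 156, and at discontinuation. Protocol 1.3 adds weeks 182, 208 and 234 and visit 98.

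**Size-adjusted analysis.** Protocol Table 9-2 has four echo SDS rows. The first is "Derived as the IVSed SDS value at baseline week 0 subtracted from IVSed SDS value at week 26 (visit 7) for Turner syndrome" and the last is "Derived as the LVIDes SDS value at baseline week 0 subtracted from LVIDes SDS value at week 26 (visit 7) for Turner syndrome"; the two between follow the same pattern. SAP Appendix 1 repeats all four, for example "Derived as the LVIDed SDS value at baseline week 0 subtracted from LVIDed SDS value at week 26 (visit 7) for Turner syndrome". SAP Table 2 lists the titles without an indication, such as "Change in interventricular Septum end diastole (IVSed) SDS", also ending at week 26. SAP 4.8 declares no change from the protocol.

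**Other echo output for NS.** Protocol 9.3.5 and SAP 4.5 plan a summary by time of assessment and a tabulation of the investigator's evaluation. No adjustment for body size is mentioned.

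**Baseline.** The SDS rows start at week 0, but no TTE is scheduled then. Section 8.2.4 says: "Any TTE performed within a month prior to screening can be used as baseline data".

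**The concern.** The SDS is planned for the indication with no stated numeric input and is absent for the indication that has it. A programmer working from the text would produce no echo SDS for NS.

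Protocol 4.2 justifies the extra TS and NS monitoring by cardiovascular safety, 2.2.3.3 names hypertrophic cardiomyopathy as a feature of NS, extension period I exists for long-term safety, and there is no control group. In growing children, a rise in raw wall thickness does not show whether the heart has outpaced the body. An SDS removes growth as an explanation. It would not attribute a change to somapacitan, because the natural course of NS remains. The raw values are collected in any case, so what is lost is pre-specification: an adjusted NS analysis done later would be post hoc.

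**Working it through.** **1. Label against collection.** The four SDS variables are four of the six measures in Table 8-3, which is the NS list. Rows assigned to TS: 4 of 4 in Table 9-2 and 4 of 4 in SAP Appendix 1. Rows assigned to NS: 0.

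**2. Does other text override the label?** A sentence after Table 9-2 says that parameters are summarised for the relevant indications. It does not say which indication is relevant to which row; the row text does. The sitting-height rows name TS and ISS, which matches the flowchart's collection rule, so row labels in this table do set the population.

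**3. Time frame.** Post-baseline NS echo visits to week 156: weeks 26, 52, 78, 104, 130 and 156, so 6. With an SDS as written: 0 of 6. With the label corrected and nothing else: 1 of 6. The parameters carried to week 52 in 9.3.6 are height velocity, height SDS, height velocity SDS, IGF-I SDS and IGFBP-3 SDS; none is an echo measure. The flowchart columns are broken in the text read from PDF, so the weeks come from the eight marks in the NS row and their spacing.

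**4. Formula as printed in the protocol.**

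Numerator = ln(dimension) − intercept + ln(weight × slope).

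Suppose the coefficients are the same at both visits. The change in the numerator is then ln(dim₂/dim₁) + ln(W₂/W₁).

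- Unchanged heart, weight up 10%: 0 + ln(1.10) = 0.095.
- Wall 10% thicker, weight unchanged: ln(1.10) + 0 = 0.095.

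So growth alone would look like thickening. The equal-coefficient condition matters, because the plan says: "The intercept, slope and SD residuals are the ones corresponding to the age at visit i". Across an age boundary, the intercept, slope and residual SD need not cancel.

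**5. Formula as printed in the SAP.** The right-hand side takes ln of the SDS, not of the measured dimension. The quantity is then defined in terms of itself, and the logarithm does not exist for an SDS of 0 or below.

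**6. Growth over the two horizons (illustration only).** Height at −2 SDS, protocol Table 10-7, in cm:

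| Entry | Start | +26 weeks | +3 years | Change at 26 weeks | Change at 3 years |
|---|---|---|---|---|---|
| Girls, 10.0 y | 125.0 | 127.2 | 143.2 | 2.2/125.0 = 1.8% | 18.2/125.0 = 14.6% |
| Boys, 11.0 y | 129.8 | 132.1 | 147.2 | 2.3/129.8 = 1.8% | 17.4/129.8 = 13.4% |
| Girls, 15.0 y | 148.9 | 149.4 | 150.2 | 0.5/148.9 = 0.3% | 1.3/148.9 = 0.9% |

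For the younger entrants, most growth falls after the week at which the SDS rows end.

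**The case against.** The label looks like a slip. If numbers exist only for NS, the rows can be run only on NS, and the week 26 harm is a wording correction. The outputs sit among other parameters in a study that tests no hypothesis. NS echo is already summarised and graded by visit, and a data monitoring committee reviews accumulating safety data. All of this stands. It limits the weight of the point, but it does not make the written rule right.

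Five stronger readings are tempting, and the documents do not support them.

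- *NS has no echo analysis.* It has one; what is missing is adjustment for size.
- *TS values are not recorded, so the TS rows should be deleted.* Section 8.2.4 states what is recorded for NS and is silent on TS. The eCRF is not among the documents. Deleting TS could remove a planned analysis in a population with known cardiovascular disease.
- *The formula is proven wrong throughout.* The equations were read from PDF and lost brackets are possible; one SAP equation prints a truncated variable name. The right form depends on the cited reference, which is not available here. Whether the slope belongs inside the logarithm is likewise a question for that reference.
- *The height percentages measure the bias in wall thickness.* They are heights on a general-population line, while the planned adjustment uses weight, and nothing in the documents links either to wall thickness.
- *The cut-off of the on-treatment set at visit 7 is an echo defect.* It affects all later safety data. It matters here only because extended rows need a data set that reaches the later visits.

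**Conclusion.** The point holds and should be corrected, but it is not critical. As written, NS has no size-adjusted echo output at any of 6 scheduled post-baseline visits to week 156, nor at the extension II visits. Confidence is high on the label and the time frame. On the formula, the documents support a need to check: the printed sign of the weight term and the SAP's logarithm of an SDS cannot both be left as they stand.

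The size is modest: descriptive results for about 10 NS participants, with no effect on the primary endpoint. The 6 visits are scheduled slots. Treatment stops at near adult height or growth-plate closure, so older entrants may not reach the later ones, and they have less growth to adjust for. The illustrative 3-year figures run from 0.9% to 14.6% depending on entry age.

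**What to change.** 1. In the four echo SDS rows of protocol Table 9-2 and SAP Appendix 1, replace the TS label with Noonan syndrome, and Turner syndrome if numeric values are recorded.
2. In those rows and in SAP Table 2, set the time frame to each scheduled TTE visit up to end of treatment. Define a data points set for these summaries that does not stop at visit 7.
3. Check the formula against the cited echocardiographic reference. The whole size-predicted value (intercept plus weight term) should be subtracted from ln of the measured dimension. Replace ln of the SDS in the SAP with ln of the dimension.
4. Name the screening TTE, or the earlier one that 8.2.4 allows, as baseline. At visit 98, where a TTE but no weight is scheduled, use the last recorded weight.

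**Cost.** Wording changes, one data-set definition and a few more derived outputs: at most 4 parameters × 6 visits × 10 participants = 240 values to week 156, against 4 × 1 × 10 = 40 if only the label is corrected. No new procedure is needed. Table 9-2 already runs near adult height to end of treatment, and the SAP is written to protocol version 3.0, so it needs updating for extension period II anyway. The downside is a weight carried forward at visit 98.
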